Interaction of Melatonin and MTNR1B Genotype on Glucose Control - Study 1

NCT02642640

October 21, 2025

Study Protocol

Using a randomized, double-blind, placebo-controlled, cross-over design, we aim to determine the effects of 5 mg melatonin oral administration and its interaction with *MTNR1B* (encodes the high-affinity melatonin receptor 1B) genotypes on disposition index (DI), first-phase insulin release, insulin sensitivity, and glucose tolerance, using a high-frequency intravenous glucose tolerance test (IVGTT) performed in the afternoon. Both carriers of the *MTNR1B* risk SNP and non-carriers will be randomized to the order of conditions (melatonin/placebo) in a crossover design. The Internal Drug Services will follow a randomization scheme in which participants will be block-randomized (block size equals 2) into two treatment orders (melatonin/placebo or placebo/melatonin). Men and women will be randomized equally between the melatonin and placebo groups. Participants undergo one 5-day in-laboratory stay, during which participants maintain their habitual sleep/wake cycle as they have been doing for the 2-3 weeks prior to each admission. Following each admission and after a baseline day and night, participants receive 5 mg of melatonin or placebo during Wake Period (WP) 2, ~1h before the glucose infusion of IVGTT (ensuring peak levels at the start and high levels throughout the 3-h IVGTT). After two washout days and nights, on WP4, participants receive the opposite treatment to the one received on WP2. IVGTT's begin ~1h after melatonin/placebo administrations, and a mixed meal test begin ~1h after IVGTT ends. This approach allows us to assess an unresolved question which is whether melatonin and its interaction with the *MTNR1B* risk variant have a more profound impact on peripheral insulin sensitivity or, by contrast, on pancreatic insulin secretion. Investigational Drug Services (IDS) block-randomize participants (block size 2) into two treatment orders (melatonin/placebo or placebo/melatonin). In addition to the research participants, all personnel who have contact with the participants or with the endpoint assessment are blinded (all investigators, recruitment personnel, technicians, nurses, and physicians).

Statistical methods

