We apply mixed model analysis on outcomes deduced from FSIGT, with melatonin/placebo as fixed factor, and individual as random factor (DI, insulin sensitivity, beta-cell function). To test the interaction effect with *MTNR1B* genotype, we use the same model, but include genotype (carriers vs. non-carriers) as a second fixed factor. Although genotype groups be matched for sex, age, and BMI, we test whether any of these factors are significant covariates. We also test for any order effects. Outcome variables exhibiting non-normality will be transformed as appropriate.

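### Does leaving the transformation open undermine the test of the melatonin-by-genotype interaction?

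*Combined protocol and SAP*

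**What the plan says.** The Statistical methods section is one short paragraph. It fits a mixed model with treatment as a fixed factor and individual as a random factor. For the interaction it adds: "To test the interaction effect with *MTNR1B* genotype, we use the same model, but include genotype (carriers vs. non-carriers) as a second fixed factor". It closes with the only sentence on scale: "Outcome variables exhibiting non-normality will be transformed as appropriate". It gives no transformation, no normality criterion, no statement of whether raw values or residuals are checked, and no timing relative to unblinding.

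Three other statements bear on the point.

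- The Study Protocol section sets as its aim the effect of melatonin, alone and jointly with MTNR1B "genotypes on disposition index (DI), first-phase insulin release, insulin sensitivity, and glucose tolerance". It also asks whether melatonin and the risk variant "have a more profound impact on peripheral insulin sensitivity or, by contrast, on pancreatic insulin secretion".
- On the comparability of the genotype groups, the Statistical methods section says: "Although genotype groups be matched for sex, age, and BMI, we test whether any of these factors are significant covariates". Matching does not extend to the level of the outcomes on placebo.
- On blinding, the Study Protocol section says that "all personnel who have contact with the participants or with the endpoint assessment are blinded", and it counts all investigators among them.

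**The concern.** For the overall effect of melatonin, moving from raw to log values seldom changes the direction of the answer. An interaction is different, because the scale sets the null hypothesis. On raw values the test asks whether melatonin changes the outcome by the same number of units in carriers and non-carriers. On logs it asks whether the percentage change is the same. If the genotypes differ on placebo and melatonin does something, both cannot be true.

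An open choice of scale could therefore let the same data be reported as showing that genotype modifies the melatonin effect, or as giving no evidence that it does. The rule also works outcome by outcome. The interaction for insulin sensitivity might end as a ratio and the one for insulin secretion as a difference in units, although the protocol wants to weigh one against the other.

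**Working it through.** The documents give no sample size, variance, effect size or significance level, so there is no figure of the plan to reproduce. Every input below is an assumption, with a two-sided 5% level.

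**1. Can the scale matter?** Let P and M be the placebo and melatonin levels, with subscript C for carriers and N for non-carriers. The raw interaction is (M_C − P_C) − (M_N − P_N). The log interaction is ln(M_C/P_C) − ln(M_N/P_N). Take P_N = 100 and M_N = 80.

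| Carriers, placebo to melatonin | Raw | Log |
|---|---|---|
| 70 to 56 (same 20% fall) | −14 + 20 = +6 | ln 0.80 − ln 0.80 = 0 |
| 70 to 50 (same 20-unit fall) | −20 + 20 = 0 | ln(50/70) − ln 0.80 = −0.113 |
| 70 to 52.5 (25% fall) | −17.5 + 20 = +2.5 | ln 0.75 − ln 0.80 = −0.065 |
| 100 to 75 (no placebo gap) | −25 + 20 = −5 | ln 0.75 − ln 0.80 = −0.065 |

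So the scale can create, remove or change the sign of the interaction. With equal placebo levels the sign is the same on both scales. With no melatonin effect the interaction is zero on both. Effects in opposite directions cannot be reversed. For a 20% fall in non-carriers and a carrier-to-non-carrier placebo ratio r, the signs disagree only when the carrier fall lies between 20% and 20%/r. At r = 0.7 that is 20% to 28.6%.

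**2. How often do the fixed scales disagree?** Assume 20 + 20 participants, a lognormal outcome, between- and within-person CVs of 30% and 20%, and carriers 30% lower on placebo. The interaction is tested by a t test on within-person differences. Rejection rates, with ranges over independent simulation runs:

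- Equal fall in units: raw 5.1% to 5.2%, log 22.9% to 23.8%.
- Equal 20% fall: raw 11.1% to 12.3%, log 5.0% to 5.3%.
- Falls of 30% in carriers and 10% in non-carriers: raw 30% to 31%, log 79% to 80%, with the verdicts differing in 48% to 49% of trials.
- With a 15% placebo gap and equal effects, the verdicts differ in 5% to 6%.

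**3. What does the stated rule do?** The plan transforms when non-normality appears. It does not permit taking the smaller p-value. Read the rule as a Shapiro-Wilk test at 5%, with log if flagged and raw otherwise. In the setting of step 2, pooled values are flagged in 93% to 96% of trials. Under an equal 20% fall the rule rejects in about 5% to 7%. With falls of 30% and 10% it rejects in 76%, close to always-log.

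A harsher setting uses a 40% placebo gap, a 20% fall in both genotypes, and the check applied to deviations from cell means. The two figures in each cell are for between/within log-SDs of 0.5/0.2 and 0.3/0.15.

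| Per genotype | Always raw | Always log | Stated rule | Smaller p-value |
|---|---|---|---|---|
| 15 | 12.8%, 24.0% | 4.6%, 4.7% | 6.3%, 12.4% | 14.9%, 25.8% |
| 25 | 17.7%, 35.9% | 5.4%, 4.5% | 5.8%, 10.3% | 20.6%, 38.2% |
| 50 | 34.1%, 62.5% | 5.1%, 4.8% | 5.1%, 6.3% | 36.4%, 64.8% |
| 100 | 60.2%, 91.4% | 4.6%, 4.5% | 4.6%, 4.5% | 62.5%, 93.3% |

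The rule stays far closer to always-log than to picking the favourable scale, and the gap to always-log closes as the trial grows.

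**4. Does a significant reversal occur?** With placebo levels of 100 and 60 and falls of 20% and 30%, the raw interaction is −18 + 20 = +2 and the log interaction is ln 0.70 − ln 0.80 = −0.134. At 20 + 20 the raw test rejects in 5.7% of trials and the log test in 31%. Both were significant in opposite directions in none of 20,000 runs (0.03% at 40 + 40).

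**The case for a change.** The strongest reply is that the plan states no such rule. It does not say Shapiro-Wilk, log or residuals, so the reassuring error rates belong to one reading of it. If normality were checked on within-person differences, only about 32% to 34% of trials would be flagged at 20 + 20, and the rule would reject in 9.5% under equal percentage effects. In a trial of 10 + 10 the check on pooled values flags about 68% to 69%, so chance would have a larger part in setting the scale. Even a mechanical rule leaves open, until the data are seen, whether the interaction is absolute or proportional.

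That much stands: the text is silent, and a small trial with a wide placebo gap is the least protected case. It does not show that the plan produces a wrong answer. A raw-scale rejection under equal percentage effects is a true statement about units, so it misleads only if the scale goes unreported. The documents do not say that the choice is made with treatment known; investigators are blinded, and normality can be checked without the treatment codes.

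The point about weighing sensitivity against secretion carries little. These are different physiological quantities in different units, no formal test between them is planned, and untransformed changes would not be on a common scale either.

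**Conclusion.** The concern is right in theory: scale and interaction are tied together, and the plan does not name the scale. It does not amount to a defect that calls for a change. The scale alters the null hypothesis only when carriers and non-carriers differ on placebo and melatonin has an effect, and the documents quantify neither. The striking disagreement (about 49% of trials in the least favourable case at 20 + 20 with a 30% gap) compares two fixed policies that the plan does not follow.

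A normality-triggered log transformation holds rejection at about 5% to 7% under equal percentage effects with 10 to 20 per genotype and a 30% gap. The figure was 10% to 12% in the harsher settings with 15 to 25 per genotype, and it returned to about 5% at 100. All of this rests on assumed lognormal outcomes, variances and sample sizes.

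Indices of this kind, positive and commonly right-skewed, are ones an analyst would ordinarily log. Doing so fills the gap sensibly and gives an interpretable ratio of ratios. Naming the scale in advance would be tidier, but it would mostly write down what competent analysts would do under the present wording.
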